5.3.4 Proportion of subjects who have a histological response

Histological response is defined as a decrease (improvement) in the C3G Histological Index for disease activity of at least 35% from baseline to Week 26. See Section 2.3.4 for further details.

5.3.4.1 Primary Analysis

For the responder analysis, data of the patients who had clinical significant increase or new introduction of treatments for C3G including MMF and/or prednisone after screening biopsy and prior to week 26 renal biopsy and were identified in the Modified Multiple Imputation Analysis will be imputed as non-responder after the initiation of rescue concomitant medication. The number and proportion of subjects who have a histological response will be presented for each treatment group. Differences between avacopan and placebo will be analyzed using the Cochran-Mantel-Haenszel (CMH) chi-square test.

The code used to generate the analysis will be similar to the following:

Additionally, the number and percent of subjects whose histological activity scores at week 26 had been invalidated because of a clinical significant dose increase or new introduction of medication to treat C3G including MMF and/or prednisone after screening biopsy and prior to week 26 renal biopsy will be summarized. For the responder analysis, data will be imputed as non-responder after the initiation of rescue concomitant medication. Concomitant medications
and other data such as adverse events will reviewed prior to database lock to determine if reason for medication use is considered to be for rescue.

Modified Multiple Imputation method may be explored for the proportion of subjects who have a histological response.

5.3.5 Change from baseline in urinary MCP-1:creatinine ratio during the 26 Week placebocontrolled treatment period

The same analysis as described for UPCR will be carried out for urinary MCP-1:creatinine ratio including primary and secondary analyses. Urinary MCP-1:creatinine ratio is computed at Baseline, Weeks 1, 2, 4, 12, 20, 26 during the 26 week double-blind treatment period and Weeks 28, 32, 38, 52 and 60 during the avacopan treatment and follow-up periods.

5.3.6 SF-36 v2 and EQ-5D-5L VAS and Index - Change from Baseline during the 26 Week placebo-controlled treatment period

The same analysis as described for eGFR will be carried out including primary and secondary analyses. This includes the physical component score, mental component score, and eight domains of the SF-36 v2, and the visual analogue scale and index of the EQ-5D-5L.

SF-36 v2 and EQ-5D-5L are computed at Baseline, Weeks 4, 12, 20, 26 during the 26 week double-blind treatment period and Weeks 32, 38, 52 and 60 during the avacopan treatment and follow-up period.

5.4 8-week Follow-Up Period Data

After the 52-week treatment period, there is an 8-week follow-up period during which subjects are not receiving any study treatment. Subjects visit the study centers at Weeks 54, 57 and Week 60 for the final study visit. Data collected at the follow up visit will be listed by subject and summarized by treatment group assignment in the double-blind period. Change and percent change in the efficacy parameters during the 8-week follow-up period will also be assessed to determine the off-treatment effect. No inferential statistical analyses will be conducted on the follow-up period data.

6 ANALYSIS OF SAFETY

6.1 Population

All safety parameters will be summarized using the Safety Population. All safety assessments will be based on actual treatments received by participants.

6.2 Study Drug Exposure and Compliance

Subject drug exposure will be calculated based on the study drug dispensing and return records (based on drug accountability). Avacopan plasma concentrations over the course of the study will also be used to assess compliance. The avacopan/placebo compliance will be calculated comparing the study drug dispensed and the study drug returned. The study drug exposure

(duration, total dose, and average daily dose) and compliance will be summarized and listed. If date of last dose is not available, the date of discontinuation from study will be used.

Duration of exposure is defined as the date of the last dose of study medication minus the date of the first dose of study medication plus 1. Duration of exposure to study medication will be summarized with descriptive statistics for the double-blind period, avacopan treatment period and both periods combined. Exposure data will be provided for the following intervals:

- < 26 weeks
- ≥ 26 weeks

Percent compliance to study drug will be summarized for double-blind, avacopan treatment period and both periods, calculated as follows:

Percent Compliance = $100 \times$ number of capsules taken / (6 × number of days in the specified period).

Percent compliance to the study drug regimen will be summarized by treatment group based on the Safety Population using counts and percentages of subjects with compliance in the following categories:

- <75%
- 75-120%
- >120%

For adolescent subjects, the dose of avacopan or placebo on Day 1 of the Treatment Period A will be calculated based on the body weight determined at screening. Depending on the avacopan plasma exposure (AUC_{0-6hr}) from Day 1, the dose will be adjusted as shown in Table 2. These dose adjustments will be made as soon as the plasma exposure results are available.

When adolescent subjects begin Treatment Period B (avacopan treatment period), they will receive avacopan twice daily. Starting on Day 183, their dose will be recalculated based on the body weight determined on that day according to Table 2. Depending on the avacopan plasma exposure (AUC_{0-6hr}) from Day 183 the dose will be adjusted as shown in Table 2. These dose adjustments will be made as soon as the plasma exposure results are available. If adolescent subjects were treated with avacopan in the first 26 weeks, their dose adjustment in the avacopan treatment period may be determined based on Day 183 trough concentration rather than exposure (AUC_{0-6hr}).

Table 2. Avacopan/Placebo Starting Dose and Dose Adjustments Based on Avacopan Plasma Exposure in Adolescent subjects

Body weight	Avacopan/Placebo Dose on Day 1 and Day 183, respectively	Avacopan Plasma AUC _{0-6hr} (ng•hr/mL) on Day 1 (or Day 183 if the subject was on placebo in the first 26 weeks)	Avacopan Dose Adjustment
<40 kg (88 lb)	10 mg (1 capsule) twice daily	≥351	None
		<351	Increase dose to 20 mg (2 capsules) twice daily
40-55 kg (88-121 lb)	20 mg (2 capsules) twice daily	351 to 699	None
		<351	Increase dose to 30 mg (3 capsules) twice daily
		>699	Decrease dose to 10 mg (1 capsule) twice daily
>55 kg (121 lb)	30 mg (3 capsules) twice daily	≤699	None
		>699	Decrease dose to 20 mg (2 capsules) twice daily

For adolescents, the formula will be altered to be consistent with the number of capsules taken daily, e.g., if the avacopan dose was 10 mg twice daily, the formula would be:

 $100 \times$ number of capsules taken / (2 × number of days in the specified period).

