4.4. Removal of Patients from Therapy

Investigators must clearly distinguish between discontinuation of study drug treatment (avacopan or placebo) and withdrawal from the study. Patients who discontinue study drug treatment or who initiate medication changes (including those prohibited by the protocol that comprise treatment failure) will not be automatically withdrawn from the study, but all efforts must be made to continue to follow the patients for all regularly scheduled visits.

Investigators must take appropriate measures to make sure that patients are motivated to comply with all requirements of the protocol in order to minimize the amount of missing data. Patients who discontinue study treatment early or initiate medication changes (including those prohibited by the protocol) should continue to be followed for all regularly scheduled visits for safety and efficacy assessments. Investigators and their staff must take measures to actively maintain contact with their patients in the study, such as telephone calls, texts, or emails between visits, and offers for transportation support to visit the study site.

Patients may be withdrawn from the study for only one of the following two reasons:

1. Patient withdrawal of consent to contribute additional outcome information;
2. Loss to follow-up.

Patients may discontinue study drug treatment for any of the following reasons:

1. Patient withdrawal of consent;
2. The Investigator may discontinue study drug treatment if, in his/her clinical judgment, it is in the best interest of the patient;
3. The Sponsor may request discontinuation of study drug treatment for safety reasons. If a patient develops any of the following lab abnormalities:

If a patient develops ALT or AST $>3x$ ULN, additional testing should be performed immediately and repeated in one week to assay for total and fractionated serum bilirubin concentration, serum albumin concentration, and prothrombin time or INR, in addition to repeat transaminase (ALT, AST) testing. In addition, if a patient develops Grade 3 or greater increased hepatic transaminases (>5 times the upper limit of normal), or if a patient develops Grade 2 or greater increased transaminases (>3 times the upper limit of normal) with elevation of bilirubin to >2 times the upper limit of normal, dosing with study drug must be paused in this patient.

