Study medication must be permanently discontinued ([FDA Guidance 2009](#)) if any of the following markers of hepatic injury and/or impaired liver synthetic function are observed, and cannot be attributed to a reversible etiology unrelated to study medication (e.g., cholelithiasis):

- ALT or AST $>8x$ ULN
- ALT or AST $>5x$ ULN for more than 2 weeks
- ALT or AST $>3x$ ULN and (Total Bilirubin $>2x$ ULN or INR >1.5)
- ALT or AST $>3x$ ULN with the appearance of fatigue, nausea, vomiting, right upper quadrant pain or tenderness, fever, rash, and/or eosinophilia ($>5\%$)

If a patient develops Grade 3 or greater leukopenia (WBC count $<2 \times 10^9/L$) or neutropenia ($<1 \times 10^9/L$), or Grade 4 lymphopenia ($<0.2 \times 10^9/L$), then study drug (avacopan or placebo) must be paused in this patient. In addition, if a patient develops Grade 2 leukopenia (WBC count $<3 \times 10^9/L$, but $\geq 2 \times 10^9/L$), the patient must be followed closely for infection and for further significant reduction (reduction by an additional $0.5 \times 10^9/L$ or more, or to $<2 \times 10^9/L$) in WBC count; if either occurs, then study drug must be paused in this patient. Study drug may be resumed only if the abnormal value returns to normal and the Investigator deems resumption to be appropriate.

If a patient develops Grade 3 or worse CPK increase (>5 times the upper limit of normal), dosing with study drug must be paused in this patient. Study drug may be resumed only if the CPK returns to normal levels.

Patients who experience deteriorating renal function based on an increase in serum creatinine of at least 50% (confirmed by a repeat measurement after at least 2 weeks) which is otherwise not explained (e.g., dehydration, new medication), or an increase in proteinuria of >3 g/g creatinine (confirmed by a repeat measurement after at least 2 weeks) from Screening or baseline during the 52-week treatment period, will exit the treatment phase of the study and be treated at the discretion of their physician. The increase of serum creatinine or proteinuria will be calculated from the higher value that is measured either at Screening or baseline. They will remain in the study for follow up and complete the remaining study visits and procedures. If a patient refuses further study participation, the Early Termination visit procedures will be performed, if possible. These patients will be considered treatment failures.

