3.2.4 Per Protocol Population

The Per Protocol (PP) Population will consist of ITT subjects who receive at least one dose of study drug and do not have protocol deviations that could significantly affect the interpretation of the results for the primary endpoints.

The following aspects will be relevant for consideration of subjects to be excluded from the PP analysis:

- Subjects with significant protocol deviations regarding inclusion and exclusion criteria that may impact evaluation of the primary endpoints.
- Subjects who did not have week 26 with renal biopsy
- Subjects with significant lack of compliance of study medication administration (avacopan /placebo) defined as: All subjects who were <75% compliant overall during the 26-week Treatment Period A based on study medication accountability records.
- Subjects with introduction of new treatment medications for C3G such as Mycophenolate mofetil (MMF) and glucocorticoids after the screening biopsy and prior to week 26 renal biopsy such that the screening renal biopsy is done off immunosuppressant medication and the week 26 renal biopsy is done on immunosuppressant medication.
- Subjects with clinically significant increase in immunosuppressant dose (MMF, Prednisone) during the study that may impact renal biopsy results significantly.
- Subjects whose data could have been significantly impacted by COVID-19.

Subjects to be excluded from the PP Population will be identified and documented prior to the database lock and unblinding for analysis. A subject's data could be partially excluded from analysis depending on when the deviation occurred. For example, if a deviation occurred during the avacopan treatment period that did not impact the data from the double-blind period, only the data during the avacopan treatment period will be excluded.

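### SAP 6.2 dates a missing last dose by study exit instead of drug discontinuation, and its compliance formula has no rule for ordered pauses or for dose changes within a period

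*SAP*

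**What the plan says.** SAP 6.2 sets duration by calendar dates: "Duration of exposure is defined as the date of the last dose of study medication minus the date of the first dose", plus one day. Its fallback is: "If date of last dose is not available, the date of discontinuation from study will be used". The amount of drug comes from accountability: "Subject drug exposure will be calculated based on the study drug dispensing and return records". Durations are tabulated as below 26 weeks or at least 26 weeks.

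Percent compliance is 100 × capsules taken, divided by 6 × the "number of days in the specified period". For younger patients the SAP adds: "For adolescents, the formula will be altered to be consistent with the number of capsules taken daily, e.g., if the avacopan dose was 10 mg". In that example, with two doses a day, the multiplier becomes 2. Compliance is tabulated below 75%, 75–120% and above 120%. SAP 3.2.4 lists among the matters to weigh for per-protocol exclusion: "All subjects who were <75% compliant overall during the 26-week Treatment Period A based on study medication accountability records".

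Protocol 4.4 says: "Investigators must clearly distinguish between discontinuation of study drug treatment (avacopan or placebo) and withdrawal from the study". It asks that patients who stop drug keep attending scheduled visits. Of those taken off treatment for worsening renal function it says: "They will remain in the study for follow up and complete the remaining study visits and procedures". It also requires dosing to be paused for listed liver, white-cell and CPK findings, and sets no maximum length for a pause.

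**The concern.** The fallback uses the date of one event to stand for another that the protocol keeps apart. When a patient stops drug and stays under observation, all the time off drug before study exit is counted as exposure. That distorts the duration summaries and the 26-week split, which are read alongside the safety data.

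The compliance figure has a related weakness. A patient who obeys a required pause loses compliance for each paused day, although nothing was prescribed on those days. The same 75% figure feeds the per-protocol review in SAP 3.2.4 and, for Period B, an optional sensitivity analysis in SAP 5.2.2. For adolescents the formula is illustrated with one constant daily count, yet Table 2 can change that count within a period, so two programmers could score the same patient differently.

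**Working it through.** The plan gives no computed exposure or compliance figure to reproduce, so the check applies its formulas to illustrative patients.

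**Inputs.** Period A is 182 days (Protocol 3.4). The first dose is on Day 1 (SAP 3.1.1), so duration equals the study day of the last dose. Weeks 26 and 52 are Days 183 and 365 (Protocol 6.11, 6.19). An adult takes 6 capsules of 10 mg a day. The cut-offs are 75% and 26 weeks = 26 × 7 = 182 days. Stop days, pause lengths and dose-change days are assumptions.

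**1. Missing last-dose date.** True last dose on Day 57, last-dose date not recorded:

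- Left the study on Day 183: excess 183 − 57 = 126 days; ratio 183/57 = 3.2.
- Left the study on Day 365: excess 365 − 57 = 308 days; ratio 365/57 = 6.4, for both periods combined.

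Either date moves the patient from below 26 weeks to at least 26 weeks. With a true stop at Day 113 the ratios are 183/113 = 1.6 and 365/113 = 3.2.

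Total dose does not move: 57 × 6 × 10 mg = 3,420 mg. If average daily dose divides that total by the substituted duration, 3,420/57 = 60 mg becomes 3,420/183 = 18.7 mg or 3,420/365 = 9.4 mg. Duration is overstated and average daily dose is understated.

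**2. Required pauses.** With every permitted capsule taken and *p* paused days, compliance = 6 × (182 − *p*) / (6 × 182) = 1 − *p*/182.

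- *p* = 14: 92.3%; *p* = 28: 84.6%.
- *p* = 45: 137/182 = 75.3%; *p* = 46: 136/182 = 74.7%.

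With adherence *a* on the other days, the score falls below 75% when *p* > 182 × (1 − 0.75/*a*). That is 39 days at 95%, 31 at 90%, 22 at 85% and 12 at 80%.

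**3. Adolescent dose change.** A fully adherent patient has 14 days on the starting count and 168 on the adjusted count. The last column varies the time on the starting count from 7 to 42 days, because the documents give no day for the change.

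| Table 2 change (capsules a day) | Capsules taken | Starting count as divisor | Adjusted count as divisor | Adjusted count, 7–42 days |
|---|---|---|---|---|
| <40 kg, 2 to 4 | 14×2 + 168×4 = 700 | 700/364 = 192.3% | 700/728 = 96.2% | 88.5–98.1% |
| 40–55 kg, 4 to 6 | 14×4 + 168×6 = 1,064 | 1,064/728 = 146.2% | 1,064/1,092 = 97.4% | 92.3–98.7% |
| 40–55 kg, 4 to 2 | 14×4 + 168×2 = 392 | 392/728 = 53.8% | 392/364 = 107.7% | 103.8–123.1% |
| >55 kg, 6 to 4 | 14×6 + 168×4 = 756 | 756/1,092 = 69.2% | 756/728 = 103.8% | 101.9–111.5% |

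On the adjusted count no early change falls below 75%; an increase would have to come after about Day 91 (<40 kg) or Day 136 (40–55 kg). A late decrease at 40–55 kg can exceed 120% although every prescribed capsule was taken. Summing the prescribed count day by day gives 100% in every row.

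**The case against.** **The fallback may rarely be used.** It applies only when the last-dose date is missing. Protocol 7.3 requires the last dose before each PK sample to be recorded, including at Week 52, and Protocol 5.8 has capsule counts from Week 4 to Week 52. This limits how often the rule is used, not whether it is right. Loss to follow-up is one of only two permitted reasons for withdrawal in Protocol 4.4, and such patients plausibly lack the date.

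**Completers.** A reader might infer that anyone followed to Week 60 is affected: a Week 10 stopper credited with 60 × 7 = 420 days instead of 70, or a completer gaining the 56 follow-up days. That needs completion to be read as discontinuation from study. Protocol 9.1 defines completion, and Protocol 8.7.1 reports it separately from early withdrawal. Read literally, the fallback does not reach these patients.

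**Adolescents.** A reader might infer that dose reductions under Table 2 are scored as non-compliance. The SAP adapts the formula for adolescents and nowhere fixes the divisor at the starting count. Only the lack of a rule for a change within the period stands.

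**Per-protocol exclusion.** A reader might infer that paused patients are wrongly dropped. SAP 3.2.4 lists the 75% figure for consideration, with decisions documented before unblinding. It is also legitimate to treat a patient off drug for a quarter of Period A as under-exposed. What stands is that the figure does not tell the reviewers whether low intake was ordered or chosen. Nothing in the documents supports a difference in pauses between arms.

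**Conclusion.** The point holds in a limited form. The last-dose fallback conflicts with Protocol 4.4 and can overstate duration several-fold for a patient who stops drug, has no last-dose date and later leaves the study. The compliance formula penalises required pauses and is silent on dose changes within a period; the first can lead to a patient being flagged, and the second leaves the score undefined.

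The reach is modest: descriptive exposure and compliance tables, and a supportive population. The primary analysis uses the ITT population in the elevated C5b-9 stratum (SAP 5.2.1) and neither figure enters it.

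The sizes rest on assumptions. The days in Period A are taken as 182, since the SAP does not say whether planned or actual days are meant. The number of missing dates, the pause lengths and the timing of dose changes are not given, so the examples show what the rules can do, not how often they will.

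**What to change.** Amend SAP 6.2 as follows:

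- **Last-dose date.** If missing, use the recorded date of study-drug discontinuation; failing that, the date supported by the last dispensing or return record. Cap it at the end of that patient's treatment period. A fixed Week 52 cap would be unsuitable, because SAP 3.1.8 foresees extended randomized treatment where a biopsy was delayed.
- **Compliance.** Divide capsules taken by capsules prescribed over the whole specified period, using the adolescent daily count in force on each day. Remove only protocol-ordered temporary pause days, and state how a pause that is never lifted is counted. Keep days after permanent discontinuation in the denominator. Counting only from first to last dose would score a fully adherent patient who stops for good at Week 10 as 100% instead of 70/182 = 38.5%, and SAP 3.2.4 has no separate criterion for stopping drug early.
- **Pauses.** Report pause days separately, so that the blinded per-protocol review in SAP 3.2.4 can see why intake was low.

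The cost is SAP wording and derivation code. The small downside is that pause and dose-change dates must be read from the dosing records.

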6.3 Adverse Events

Adverse event results will be provided including number of events and percentages of subjects (subject incidence) affected for the 3 Safety Populations (see 3.2.3 for definitions) separately including the following:

- All treatment emergent serious adverse events by SOC and preferred term
- All treatment emergent serious adverse events by decreasing order of frequency by preferred term
- All treatment emergent non-serious adverse events by SOC and preferred term
- All treatment emergent non-serious adverse events by preferred term by decreasing order of frequency
- All treatment emergent serious and non-serious adverse events by SOC

• All treatment emergent serious and non-serious adverse events by decreasing order of frequency by preferred term

Adverse events will be coded using the Medical Dictionary for Regulatory Activities (MedDRA) Version 20.1.

TEAEs for the Safety Population in each period are defined as an event with a start date on or after the first study drug treatment in each period and up to the final observation in each period. Treatment periods for analysis of adverse event are defined in Section 3.2.3. TEAEs for the All Avacopan Treated Population are defined as an event with a start date on or after the first dose of avacopan up to the final visit.

Adverse events will be listed by treatment group, including all available information of interest such as onset and resolution dates, study day of onset and resolution relative to first dosing day, duration, severity, seriousness, causal relationship to study medication per the investigator, action taken with study medication, and outcome. Separate listings will be provided for TESAEs, TESAEs and TEAEs leading to discontinuation of study drug, and TEAEs of interest.

TEAEs of interest include hepatic enzyme elevations, hypersensitivity Standardized MedDRA Queries (SMQ), infections, decrease in white blood cell count and elevations in creatine phosphokinase (CPK).

The severity of AEs was assessed by the investigator using the following protocol definitions:

- Mild (Grade 1): no limitation of usual activities
- Moderate (Grade 2): some limitation of usual activities
- Severe (Grade 3): inability to carry out usual activities
- Life-threatening (Grade 4): an immediate risk of death
- Death (Grade 5)

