6.11. Study Week 26 (Day 183)

The Study Week 26 visit must occur within ± 7 days of the scheduled date. During this visit, the following study procedures will be performed:

- A physical examination including body weight; height will also be measured in 12 to 17 year-old patients;
- Vital signs (temperature, sitting blood pressure, heart rate) after at least 3 minutes of rest;
- A 12-lead ECG will be performed after at least 3 minutes of rest in a supine position;
- Blood samples will be collected before the morning dose for shipment to the central laboratory for a serum pregnancy test (in women of childbearing potential), serum chemistry, hematology, lymphocyte subset analysis, and PK and PD measurements. Record the date and time of blood draw;
- The date and time of the last dose of avacopan/ avacopan-matching placebo prior to collection of the PK sample will be recorded;
- The patient will be asked to take the morning dose of avacopan while at the study center;
- The time of the dosing of avacopan will be recorded;
- If the patient is 12 to 17 years old, blood samples will be taken before dosing and at Hour 0.5, 1, 2, 3, 4, and 6 after the morning dose of avacopan; plasma samples will be frozen and sent to the central laboratory for expeditious measurement of avacopan and metabolite plasma concentrations. *Note: it is important that on Day 183 the adolescent patients take the dose when instructed at the study center, NOT at home, and they should be reminded through a telephone call two days before the Day 183 visit.*
- A clean catch, midstream urine sample will be collected for urinalysis, for PD assessment, and for urine protein, urine albumin, urinary MCP-1 and urine creatinine measurement for calculation of UPCR, UACR and urinary MCP-1:creatinine ratio; the sample will be sent to the central laboratory;
- Renal biopsy, performed within -2 weeks prior to the Week 26 visit and BEFORE patient is started on open-label treatment;
- Patients will be asked to complete the SF-36 v2 and EQ-5D-5L;
- Drug accountability will be performed on the returned avacopan/ avacopan-matching placebo bottles;
- Two new bottles of avacopan will be dispensed;
- For adolescents, two new bottles of avacopan will be provided to the patient with dosing instructions according to body weight (see [Section 5.3](#));

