7.2.4. Adverse Events

An adverse event (AE) is defined as any untoward medical occurrence associated with the use of a drug in humans, whether or not considered drug related. An adverse event could therefore be any unfavorable and/or unintended sign (including abnormal laboratory findings), symptom, or disease temporally associated with the use of the drug, whether or not considered related to the drug. This definition includes intercurrent illnesses or injuries, and exacerbation of pre-existing conditions.

An unexpected adverse event is an adverse event that is not identified in nature, severity, or frequency in the current Investigator's Brochure, or that is of greater severity than expected based on the information in the Reference Safety Information listing within the Investigator's Brochure.

All adverse events occurring in patients who have been randomized to treatment will be recorded in the EDC system and will be reported in accordance with regulatory requirements. Adverse events reported prior to commencement of administration of blinded study medication will be considered pre-treatment events and will also be captured.

All adverse events will be monitored until resolution or, if the adverse event is determined to be chronic, until a cause is identified. If an adverse event remains unresolved at the conclusion of the study, a clinical assessment will be made by the Investigator and the Sponsor's Medical Monitor to determine whether continued follow-up of the adverse event is warranted.

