2.3.7 Safety Endpoints

2.3.7.1 Adverse Events

Safety endpoints include subject incidence of treatment-emergent serious adverse events, treatment emergent non-serious adverse events, and withdrawals from the study drug or clinical trial due to adverse events.

An adverse event will be considered treatment-emergent (TEAE) if the start date of the event is on or after the date of administration of the first dose of study medication. All reported adverse events will be classified by system organ class and preferred term using the Medical Dictionary for Regulatory Activities (MedDRA) (version 19.1). Treatment-emergence will also be determined based on the Safety Populations defined in Section 3.2.3.

The relationship to avacopan/placebo will be determined by the Investigator. The sponsor will perform a safety analysis based on an aggregate analysis across the safety database as well as the assessment of individual cases of interest.

A serious adverse event (SAE) is defined as any untoward medical occurrence that at any dose results in death, is life-threatening, requires or prolongs hospitalization, results in persistent or significant disability or incapacity, is a congenital anomaly or birth defect, or is an important and significant medical event that, based on appropriate medical judgment, may jeopardize the subject and/or may require medical or surgical intervention to prevent one of the other outcomes defining serious.

In addition, specific TEAEs of interest will be presented by treatment group (see Section 6.3).

2.3.7.2 Clinical Laboratory Assessments

Safety endpoints related to clinical laboratory assessments include change from baseline and shifts from baseline in all safety laboratory parameters, including blood chemistry, hematology, and urinalysis.

Clinical laboratory assessments will be performed at the visits identified in the Time and Events Table in the protocol:

- Hematology: hemoglobin, hematocrit, red blood cell (RBC) count, white blood cell (WBC) count with differential, platelet count, mean cell hemoglobin, mean cell hemoglobin concentration, mean corpuscular volume

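### An adverse event from the pre-dose Week 26 blood sample meets both period TEAE definitions and, in placebo patients, is also counted under avacopan

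*SAP*

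**What the plan says.** SAP 3.2.3 runs Period A from Day 1 to Week 26 and Period B from Week 26 to the end of study. It defines three safety populations: Period A, Period B and All Avacopan Treated. SAP 6.3 tabulates adverse events for each of them separately.

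For the two periods, SAP 6.3 defines a TEAE by a "start date on or after the first study drug treatment in each period and up to the final observation in each period". For All Avacopan it is "an event with a start date on or after the first dose of avacopan up to the final visit". The general definition in SAP 2.3.7.1 applies "if the start date of the event is on or after the date of administration of the first dose of study medication".

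For the Week 26 visit, Protocol 6.11 states: "Blood samples will be collected before the morning dose for shipment to the central laboratory". At the same visit, "The patient will be asked to take the morning dose of avacopan while at the study center". The same section asks sites to record the time of the blood draw and the time of the avacopan dose.

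**The concern.** One calendar day belongs to both periods, and on that day blood is drawn before avacopan is given. Suppose a placebo patient's Week 26 sample shows a low neutrophil count and this is reported as an adverse event with the visit date as onset. Patient and finding both belong to placebo time, yet the SAP 6.3 rules also place the event in Period B and in All Avacopan.

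White-cell decreases, hepatic enzyme elevations and CPK elevations are among the events of interest in SAP 6.3, and all of these are found by blood tests. Hematology testing was made more frequent on DMC advice (Protocol 12.3.2), so these tables will be read closely. Background immunosuppressants are allowed in both arms (Protocol 5.9), so such findings are plausible in placebo patients. Crediting them to avacopan would blur the tables meant to describe its safety.

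**Working it through.** There is no stated figure to reproduce, because the point concerns a classification rule. The check applies the rule literally to study days.

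**Inputs**
- Period limits: SAP 3.2.3.
- Inclusive start and end of each TEAE window: SAP 6.3.
- Blood draw before the dose, dose at the same visit, visit window of ±7 days: Protocol 6.11.
- Last visit: Week 60, Day 421 (Protocol 6.22).
- About 22 patients per arm in each C5b-9 stratum: Protocol 8.8 and SAP 9.

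**Step 1: the switch day.** Week 26 = 26 × 7 + 1 = Day 183.

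**Step 2: apply the windows to an event starting on day d.**

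| Start day | Period A (1 ≤ d ≤ 183) | Period B (183 ≤ d ≤ 421) | All Avacopan, placebo arm (d ≥ 183) |
|---|---|---|---|
| 182 | yes | no | no |
| 183 | yes | yes | yes |
| 184 | no | yes | yes |

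Only Day 183 meets both period definitions. If the visit falls at either edge of its window (183 − 7 = Day 176, or 183 + 7 = Day 190), the overlap is again that single visit day.

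**Step 3: try a narrower Period A.** If Period A is taken to end the day before the switch, a Day 183 event is no longer in Period A but is still in Period B and All Avacopan. A placebo patient's pre-dose finding would then count only as an avacopan event. That removes the duplication and makes the attribution worse.

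**Step 4: look for a tie-break.** SAP 6.3 lists onset date and study day, with no onset time. SAP 12.2 deals with incomplete or missing dates only. The pre-treatment rule in Protocol 7.2.4 concerns the start of blinded dosing, not the Week 26 switch. Neither document settles a complete date equal to the switch day.

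**Step 5: illustrate the scale (assumed rates, not in the documents).** Let p be the proportion of 22 placebo patients in one stratum with an adverse event dated to the pre-dose Week 26 sample. The expected number is 22p, and the chance of at least one is 1 − (1 − p)^22.

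| Assumed p | Expected patients | Chance of at least one |
|---|---|---|
| 2% | 0.44 | 36% |
| 5% | 1.1 | 68% |
| 10% | 2.2 | 90% |

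One such patient changes an incidence by 1/22 = 4.5 percentage points if former placebo patients are shown separately. With both arms of the stratum pooled, the change is 1/44 = 2.3 points. Both figures assume planned enrolment and that everyone enters Period B.

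**The case against.** The best counter-argument is textual. SAP 6.3 refers to the first treatment or first dose, not to its date, so a finding from a sample taken earlier that morning could be read as falling before it. That makes the rule open to a sensible reading, but the rule still tests a start date. The listed onset data are dates and study days, and SAP 2.3.7.1 compares a date with a date. A programmer following the SAP would include the event.

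Other limits stand and narrow the point:

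- **Which findings.** Pre-dose timing at Week 26 is documented only for blood and biopsy. A reader might infer that the examination, vital signs and ECG also come before the dose because they are listed first. The list is not chronological: the biopsy, which must precede open-label treatment, is listed after the dose.
- **Counted twice.** A reader might infer double counting within a table. The three populations are tabulated separately and overlap by design, so no event counts twice in any one of them. For patients randomised to avacopan, All Avacopan is correct and the only effect is duplication across the period tables.
- **Day 1.** A reader might infer the same fault at the first dose. The protocol sentence is "Adverse events reported prior to commencement of administration of blinded study medication will be considered pre-treatment events", which turns on when an event is reported. A central-laboratory result from the Day 1 sample could be reported after dosing, so a contradiction with the SAP is not established.
- **Draw shares.** Week 26 is one of nine post-Day 1 hematology draws in Period A. A reader might infer that about 1/9 = 11% of events are affected. That requires equal detection at every draw, which the documents do not support: Protocol 12.3.2 describes lymphopenia arising within the first two weeks of treatment.

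Part of the mitigation is also real. Listings show the onset day, and SAP 6.4 summarises central-laboratory values by visit, so a careful reader could trace a misplaced event.

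**Conclusion.** The point holds for adverse events that come from the Week 26 blood sample and are dated to the draw. Under SAP 6.3 they fall in Period A and Period B and, for patients randomised to placebo, in All Avacopan before any avacopan has been taken. The consequences are possible over-attribution to avacopan among patients who switch, and duplication across the period tables. The randomised Period A comparison is unaffected, because the present rule correctly keeps these events there.

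The overlap is one day per patient. How many events fall on it cannot be determined from the documents; the 2% to 10% rates above are illustrative. The conclusion assumes that a laboratory event is dated to its sample, which neither document states, and that the first Period B dose is taken at the Week 26 visit as planned. A patient whose first Period B dose falls on a later day than the last Period A observation has no overlap. This is worth correcting before unblinding because the stated rule gives a wrong attribution, but it does not threaten the trial's main safety comparison.

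**What to change.** Add one rule to SAP 6.3. It applies to a laboratory adverse event whose onset date is the Week 26 visit and which comes from the blood sample drawn before the first Period B dose, as shown by the recorded draw and dose times. Such an event is counted in Period A only. It is excluded from Period B and, for patients randomised to placebo, from All Avacopan. For patients randomised to avacopan it remains in All Avacopan.

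Leave every other event on that date under the present rule and flag it in the listing. Moving events of unknown time to Period B only would take placebo events out of Period A, alter the randomised comparison and create the misattribution that the rule is meant to prevent.

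The cost is a sentence of SAP text and a few lines of programming. Both times are already collected at Week 26. Because no onset time is listed for adverse events, laboratory events dated to that visit must be matched to the sample during blinded data review, which is a small extra task.
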